3.3.3.2 Cardiac Magnetic Resonance Imaging (cMRI)

Cardiac MRI imaging will be performed in all subjects aged 10 years and older at Baseline and Week 24/Premature Termination; imaging may be optionally performed in subjects under the age of 10 years. Cardiac MRI should be performed prior to the 6MWT and CPET, if done on the same day. If subject requires anti-anxiety medication in order to undergo and still follow directions (no general anesthesia) during the cMRI (without contrast), then the cMRI should be performed on a separate day from the CPET and 6MWT.

The subject's BP will be taken immediately prior to the cMRI assessment in the supine position to measure vascular parameters.

The following parameters will be evaluated:

- Right ventricular (RV) mass index
- RV ejection fraction (RVEF)
- Left ventricular (LV) ejection fraction (LVEF)
- RV end-diastolic volume (RVEDV) index
- RV end-systolic volume (RVESV) index

- RV stroke volume index
- LV stroke volume index
- RV cardiac output index

The following additional parameters may be collected:

- Flow pattern through the MPA by phase-sensitive gradient echo imaging
- Flow pattern through the RPA by phase-sensitive gradient echo imaging
- Flow pattern through the Ascending aorta by phase-sensitive gradient echo imaging
- RV:LV end-systolic diameter ratio
- Systolic septal flattening
- Right atrial size
- Presence of congenital heart disease
- Atrial or ventricular shunt

Cardiac MRI measurements from images will be analyzed by a centralized specialist reader to control for bias and to reduce inter-reader variability. The centralized specialist reader may communicate with the site and establish study specific analysis settings for assessments performed for purposes of this protocol.

3.4 NUMBER OF CENTERS

The study is a US-based multi-center study with approximately 10 centers participating.

3.5 NUMBER OF SUBJECTS

A total of 40 subjects will be enrolled in this study. Approximately 25 subjects will be enrolled between Cohort 1 and Cohort 2 of this study, and 15 subjects will be enrolled into Cohort 3.

3.6 ESTIMATED STUDY DURATION

From Screening until study completion, expected duration of subject participation is approximately 28 weeks (four week screening period and 24 week treatment period).

4 SUBJECT ELIGIBILITY

Inclusion and exclusion criteria are to be assessed during the Screening period and reconfirmed at the Baseline visit prior to the first dose of oral treprostinil. Study related procedures must be conducted during the Screening period after obtaining informed consent and assent (if applicable) to determine subject eligibility for the study.

4.1 INCLUSION CRITERIA

A subject is eligible for inclusion in this study if all of the following criteria apply:

- 1. Legal guardian informed consent and subject assent, if appropriate, to participate in the study is voluntarily given.
- 2. The subject is between 7 and 17 years of age, inclusive, on the date informed consent is signed.
- 3. *Cohort 3:* The subject must weigh a minimum of 22 kg at Screening.
- 4. The subject has a current diagnosis of PAH (WHO Group I) associated with:
 - a. Idiopathic or heritable PAH
 - b. Persistent PAH for at least one year following surgical repair of a congenital systemic-to-pulmonary cardiac shunt, congenital heart disease, or other congenital heart lesions with no clinically significant residual defects and condition is stabilized hemodynamically
 - c. PAH in subjects with unrepaired restricted atrial septal defect, ventricular septal defect, or patent ductus arteriosus; subject must have a resting postductal oxygen saturation (off oxygen) of greater than 88%
- The subject has a current diagnosis of PAH confirmed by right heart catheterization (RHC) prior to the Screening visit with the following parameters:
 - a. Mean pulmonary arterial pressure (mPAP) of ≥25 mmHg
 - b. Pulmonary vascular resistance index (PVRi) of >3 Wood Units * m²
 - c. Left ventricular end diastolic pressure (LVEDP) or pulmonary capillary wedge pressure (PCWP) of ≤15 mmHg

- 6. Cohort 1: The subject must have been receiving IV/SC Remodulin for at least 90 days without dose change for at least 30 days prior to Baseline. The IV/SC Remodulin dose will be between 25-75 ng/kg/min, inclusive, for the first five subjects in the cohort. Following a safety review, the dose range may be expanded to 25-125 ng/kg/min, inclusive, for the remaining subjects. Subjects must be receiving stable doses of all other PAH medications for at least 14 days prior to the Baseline assessments; exception for diuretics and anticoagulants as outlined in Section 4.3.1.
- 7. Cohort 2: The subject must have been receiving inhaled prostacyclin for at least 90 days and has been at the current stable dose without changes for at least 30 days prior to Baseline. Subjects must be receiving stable doses of all other PAH medications for at least 14 days prior to the Baseline assessments; exception for diuretics and anticoagulants as outlined in Section 4.3.1.
- 8. *All Cohorts:* All subjects must be optimally treated (as determined by the Investigator) with background PAH therapies (e.g., PDE-5i, ERA, soluble guanylate cyclase [sGC]) for at least 90 days and have been on a stable dose without changes (except documented weight based adjustments) for at least 30 days prior to the first dose of oral treprostinil. Subjects must be receiving stable doses of all other PAH medications for at least 14 days prior to the first dose of oral treprostinil; exception for diuretics and anticoagulants as outlined in Section 4.3.1.
- 9. The subject is willing and able to swallow intact tablets whole without chewing, breaking, or splitting.
- 10. The subject is willing and able to comply with the dietary requirements associated with the oral treprostinil dosing regimen.
- 11. The subject must be on stable doses of other medical therapy for 14 days prior to Baseline visit with no dose adjustments, additions, or discontinuations. Dose changes of diuretics are allowed if within the usual dose adjustments prescribed for the subject. Anticoagulants may be adjusted, but not discontinued or added, within 14 days of

TDE-PH-206

Baseline. Temporary discontinuation of anticoagulants when related to study related procedures is allowed.

- 12. Females of childbearing potential include any female who has experienced menarche. Females of childbearing potential must practice true abstinence from intercourse, have an IUD, or must use two different forms of highly effective contraception for the duration of the study, and for at least 30 days after discontinuing oral treprostinil. Medically acceptable forms of effective contraception include approved hormonal contraceptives (such as birth control pills) or barrier methods (such as a condom or diaphragm) used with a spermicide. For females of childbearing potential, a negative urine pregnancy test is required at Baseline prior to oral treprostinil administration. Males participating in the study must use a condom during intercourse for the duration of the study, and for at least 48 hours after discontinuing oral treprostinil.
- Subjects with a history of metallic implants, prior neurosurgical clip placement, or other potential contraindications to cMRI may be individually evaluated per site standard operating procedures for MRI performance.
- 14. In the opinion of the Principal Investigator, the subject and/or legal guardian is able to communicate effectively with study personnel, and is considered reliable, willing and likely to be cooperative with protocol requirements, including attending all study visits.

4.2 EXCLUSION CRITERIA

A subject is not eligible for inclusion in this study if any of the following criteria apply:

- The subject has a diagnosis of large unrestrictive ventricular septal defect or patent ductus arteriosus, Eisenmenger syndrome, congenital diaphragmatic hernia, or a chronic lung disease, such as bronchopulmonary dysplasia, or interstitial lung disease.
- 2. The subject has a current disease severity of Panama functional class IIIb or IV.
- 3. The subject has previously been exposed to oral treprostinil.

Version: Amendment 2_FINAL_01Sep2016

- 4. *Cohort 1:* the subject has had previous intolerance to treprostinil or epoprostenol due to systemic adverse effects that resulted in discontinuation of therapy. This does not include site pain reactions or central venous catheter-related blood stream infections.
- 5. Cohort 1 and 2: the subject is receiving IV/SC Remodulin or Tyvaso (as the inhaled prostacyclin) for any other disease or condition other than the treatment of PAH in accordance with the IV/SC Remodulin or Tyvaso package inserts (i.e., eligible subjects must have a WHO Group I PAH classification as defined in inclusion criteria #4).
- 6. *Cohort 3:* the subject has been previously exposed to a prostacyclin within 30 days of Screening, with the exception of vasoreactivity testing.
- 7. The subject is pregnant or lactating.
- 8. The subject has a current diagnosis of uncontrolled sleep apnea as defined by their physician.
- The subject has severe renal insufficiency as defined by an estimated creatinine clearance (CrCl) <30 mL/min (Schwartz Formula) or the requirement for dialysis at Screening.
- 10. The subject has moderate to severe hepatic dysfunction; defined as elevated liver function tests (AST or ALT) greater than or equal to three times the upper limit of normal at Screening, or Child Pugh class B or C hepatic disease.
- The subject has clinically significant anemia as defined by a hemoglobin and/or hematocrit level <75% of the lower limit of normal ranges according to age and gender.
- 12. The subject has Down Syndrome.

- The subject has uncontrolled systemic hypertension as evidenced by a systolic or diastolic blood pressure greater than the 95th percentile for age, height, and gender at Screening or Baseline.
- 14. The subject and/or legal guardian has/have an unstable psychiatric condition or is/are mentally incapable of understanding the objectives, nature, or consequences of the trial, or has any condition in which the Investigator's opinion would constitute an unacceptable risk to the subject's safety.
- 15. The subject has an active infection, or has any other cardiovascular, liver, renal, hematologic, gastrointestinal, immunologic, endocrine, metabolic, or central nervous system disease or condition that, in the opinion of the Investigator, may adversely affect the safety of the subject or interfere with the interpretation of study assessments.
- 16. Subject is actively listed for transplantation.
- 17. The subject is receiving an investigational drug, has an investigational device in place or has participated in an investigational drug or device study within 30 days prior to Baseline. Participation in an observational study does not disqualify a potential subject from study participation.

4.3 PRESCRIBED THERAPY

4.3.1 Concomitant Medications

Cohort 1:

Subjects must have been receiving IV/SC Remodulin for at least 90 days prior to Baseline and have been at the current dose without changes for at least 30 days prior to Baseline.

Cohort 2:

Subjects must have been receiving inhaled prostacyclin for at least 90 days with no dose changes for at least 30 days prior to Baseline.

TDE-PH-206

All Cohorts:

Subjects must be optimally treated (as determined by the Investigator) with background PAH therapies (e.g., PDE-5i, ERA, sGC) for at least 90 days and have been on a stable dose without changes (except documented weight based adjustments) for at least 30 days prior to Baseline. All attempts should be made to avoid dose adjustments of current PAH background therapy(ies) or the addition of another PAH therapy from Baseline to Week 24.

Subjects must be receiving stable doses of all other medications for at least 14 days prior to the Baseline assessments. Dose changes of diuretics are allowed if the dose adjustments are within the usual dose adjustments prescribed for the subject. Dose adjustments of anticoagulants are permitted at any time during the study, as needed. Anticoagulants may be temporarily discontinued during the study if necessary for the safety of study related or medically required procedures (e.g., RHC).

For the purposes of the 6MWT, if the subject was assessed at Baseline using oxygen therapy, then all 6MWTs during the 24-week study should be conducted with the same oxygen flow rate and mode of administration. All concomitant medications taken during the conduct of the study, including those taken for AEs or other medical events, must be recorded in the subject's source documents and transcribed as required to the eCRF. Dose changes of concomitant medications will not be captured in the eCRF.

5 SUBJECT ENROLLMENT

5.1 TREATMENT ASSIGNMENT

All subjects will receive treatment with oral treprostinil. Subjects will be enrolled into a cohort based on their current PAH treatment regimen.

5.2 RANDOMIZATION

No randomization will occur.

5.3 BLINDING

This an open-label study; all subjects will receive oral treprostinil extended release tablets.

5.4 STOPPING CRITERIA

If any of the following events occur within the four weeks following the first dose of drug oral treprostinil given for all cohorts, the subject should be transitioned back to IV/SC Remodulin (Cohort 1 subjects only) or tapered off oral treprostinil, as appropriate, and discontinued from the study:

- Unplanned hospitalization as a result of worsening PAH
- Clinically significant worsening in PAH symptoms or signs, which the Investigator feels requires a change of current therapy.

If two or more of the first five subjects in any cohort meet the stopping criteria, the data will be reviewed by a Data Safety Monitoring Board (DSMB) prior to enrolling additional subjects into that cohort.

If any of these events happen after the first four weeks of the study, it is not required that a subject be removed from the study. The Investigator will determine whether it is safe for a subject to remain in the study.

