10.4 INTERIM ANALYSIS

A DSMB will be established for the study, composed of approximately two to three independent members including physicians knowledgeable in the treatment of PAH and pediatric PAH. Once five subjects have enrolled in Cohort 1 and transitioned from IV/SC Remodulin, the safety data will be reviewed by the DSMB. The IV/SC Remodulin dose will be between 25-75 ng/kg/min, inclusive, for the first five subjects enrolled in Cohort 1. Following the DSMB safety review, the dose range may be expanded to 25-125 ng/kg/min, inclusive, for the remaining subjects.

Additionally, if two or more of the first five subjects within any cohort meet the pre-specified stopping criteria, the data from that cohort will be reviewed prior to enrolling additional subjects into that cohort.

Analysis of pharmacokinetic samples may be performed, as warranted, to guide dosing.

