## 5 SEQUENCE OF PLANNED ANALYSES

A Data Safety Monitoring Board (DSMB) will meet after 5 subjects have enrolled in Cohort 1 and transitioned from IV/SC Remodulin to evaluate any safety concerns. The safety data will be prepared according to the separate DSMB analysis plan. The IV/SC Remodulin dose will be 25 to 75 ng/kg/min, inclusive, for the first 5 subjects enrolled in Cohort 1. Following the DSMB safety review, the dose range may be expanded to 25 to 125 ng/kg/min, inclusive, for the remaining subjects.

Additionally, if 2 or more of the first 5 subjects within any cohort meet the pre-specified stopping criteria, the DSMB will review the data prior to enrolling additional subjects into that cohort.

Analysis of PK samples may be performed, as warranted, to guide dosing.

Upon completion of all study subjects, after all outstanding queries are resolved and all data management quality assurance procedures are completed, the database will be locked. All data from the electronic case report form (eCRF), as well as data transmitted from external vendors for laboratory and PK presentation, will be included in the locked database. All final analyses will be performed on the final locked database.

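### If Cohort 1 is opened above 75 ng/kg/min, the protocol and SAP contain no DSMB enrolment-pause trigger that can count the newly admitted subjects

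*Protocol*

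**What the plan says.** Protocol Section 5.4 names two individual stopping events: unplanned hospitalisation for worsening PAH, and clinically significant worsening that the investigator judges to need a change of therapy. They lead to discontinuation "If any of the following events occur within the four weeks following the first dose" of oral treprostinil. Above them sits one cohort-level rule: "If two or more of the first five subjects in any cohort meet the stopping criteria", then "the data will be reviewed by a Data Safety Monitoring Board (DSMB) prior to enrolling additional subjects into that cohort". The synopsis and Sections 3.1 and 10.4 repeat it. SAP Section 5 has the same scope: "if 2 or more of the first 5 subjects within any cohort meet the pre-specified stopping criteria".

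Cohort 1 entry is staged by current Remodulin dose. Protocol Section 10.4: "The IV/SC Remodulin dose will be between 25-75 ng/kg/min, inclusive, for the first five subjects enrolled in Cohort 1". After the DSMB has looked, "the dose range may be expanded to 25-125 ng/kg/min, inclusive, for the remaining subjects". Inclusion criterion 6 in Section 4.1 agrees: "Following a safety review, the dose range may be expanded to 25-125 ng/kg/min, inclusive, for the remaining subjects". The only DSMB review with a fixed time is the one between these stages: "Once five subjects have enrolled in Cohort 1 and transitioned from IV/SC Remodulin, the safety data will be reviewed by the DSMB".

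SAP Section 5 says that the data for this review are prepared under a separate DSMB analysis plan. That plan is not among the documents.

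**The concern.** The two provisions seem to have been written independently of each other. One makes independent review a condition of admitting children on higher Remodulin doses. The other spends its count on the five subjects who, by that same condition, cannot be on those doses. Once the range widens, events among the newly admitted children cannot set off the stated trigger, however many occur.

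What is at stake is a pre-specified obligation. If several of these children were hospitalised or worsened within four weeks, nothing in the protocol or SAP would require enrolment to pause or the DSMB to meet. Both documents (Protocol 10.2, SAP 6) say the study should support safety conclusions about transition from moderate to high Remodulin doses, so these subjects are part of the question being asked.

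**Working it through.** **Coverage.** This part needs no assumption about event rates.

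| Question | Answer | Source |
|---|---|---|
| Who counts towards the trigger in Cohort 1? | Subjects 1-5 | Protocol synopsis, 3.1, 5.4, 10.4; SAP 5 |
| At what dose may subjects 1-5 enter? | 25-75 ng/kg/min, 75 included | Protocol synopsis, 3.1, 4.1, 10.4; SAP 5 |
| Who may enter above 75, up to 125? | Subject 6 onward, if the range is expanded | Same sections |
| When is the scheduled DSMB review? | After five subjects have enrolled and transitioned, before any expansion | Protocol 3.1, 10.4; SAP 5 |
| Is the count restarted, or a second review scheduled? | Not in either document | - |

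Subjects 1-5 and subjects 6 onward do not overlap, so the chance that events above 75 fire the trigger is 0 at any event rate. Events in the first five could still pause the whole cohort, but events in the higher-dose subjects cannot.

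**What still applies to those subjects.**
- Individual stopping criteria (Protocol 5.4): act on one subject at a time.
- All unplanned hospitalisations reported as SAEs (9.1.4), and SAEs sent to the sponsor within 24 hours (9.4): inform the sponsor, with no count.
- Reports of serious, unexpected and possibly attributable events to regulators and investigators (9.6): no enrolment consequence.
- Termination in the opinion of the investigator or sponsor (8.2): discretionary, with no threshold and no stated DSMB role.

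**How many subjects.** Protocol 10.2 plans 10-15 per cohort. Beyond the first five that leaves 10 - 5 = 5 to 15 - 5 = 10 in Cohort 1. The widened range still starts at 25, so only some of these would exceed 75. The documents do not allow that share to be estimated.

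**What the existing count would do if applied there.** The plan states no operating characteristic and no event rate, so there is no figure to reproduce and the rates are assumptions. With X ~ Binomial(5, p):

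P(X ≥ 2) = 1 - (1-p)^5 - 5p(1-p)^4

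For p = 0.20: 1 - 0.3277 - 0.4096 = 0.263.

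| Assumed 4-week event rate above 75 | Trigger as written | Two-of-five count in that stratum |
|---|---|---|
| 5% | 0 | 0.02 |
| 10% | 0 | 0.08 |
| 20% | 0 | 0.26 |
| 30% | 0 | 0.47 |
| 40% | 0 | 0.66 |

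For an outer bound, suppose all later Cohort 1 subjects entered above 75. The chance of two or more events among them is then as follows. None of these events would activate the stated rule.

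| Assumed rate | 5 later subjects | 10 later subjects |
|---|---|---|
| 10% | 0.08 | 0.26 |
| 20% | 0.26 | 0.62 |
| 30% | 0.47 | 0.85 |

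**The case against.** The strongest reply is that the DSMB is set up for the study as a whole and works to an analysis plan that we have not seen. Neither document says its role ends after the first review. This stands. It limits the claim to the protocol and SAP and lowers confidence to moderate.

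A second reply is that the rule is a uniform early-subject rule: subject 6 onward in Cohorts 2 and 3 is outside it too. That is correct, and the passages do not contradict each other. The difference in Cohort 1 is that a pre-specified widening of the entry range follows the counted five, so those five cannot represent what comes after.

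A third reply is that a two-of-five count is weak. At a 20% event rate it stays silent with probability 1 - 0.26 = 0.74, and five subjects above 75 may never accrue. Both points stand, but the threshold is the protocol's own.

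Some stronger readings are tempting and are not supported:
- **That these children have no safety net beyond sponsor or investigator opinion.** The individual criteria and SAE reporting listed above still cover them, as do the inpatient start with daily assessments (7.4.1) and required contact through Week 24 (3.3.2.6).
- **That up to 20 subjects are affected.** That needs an empty Cohort 2 within the roughly 25 transition places (3.5), against a planned 10-15 per cohort.
- **That the protocol staged entry because it judged higher doses riskier.** No section gives the reason for staging.
- **That exposure rises by two thirds.** The Section 6.1.1 formula gives a 35 kg child 0.0072 x 75 x 35 = 18.9 mg/day and 0.0072 x 125 x 35 = 31.5 mg/day. It estimates a comparable oral dose for a child already stable on that Remodulin dose, so it shows no increase for any individual.

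**Conclusion.** The point holds as a gap in pre-specified oversight. In the protocol and SAP, the only cohort-level DSMB trigger cannot count a Cohort 1 subject who enters above 75 ng/kg/min, and the only scheduled DSMB review comes before such a subject can enter. This follows from the wording alone.

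Its practical size is modest and uncertain. It depends on the optional expansion taking place, on how many of about 5-10 later subjects exceed 75, and on an unknown event rate. At low rates (5-10%) a restarted count would rarely fire. At 30-40% it would fire about half to two thirds of the time, where the present text gives no trigger at all. The documents do not show that the DSMB would in fact be inactive after expansion, because its own plan may say otherwise. Confidence is moderate. The change is worth making because it is cheap and the population is children moving off parenteral therapy in an uncontrolled study.

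**What to change.** Reconcile the pause rule with the dose-range expansion in Protocol Sections 5.4 and 10.4 and SAP Section 5, with matching text in the synopsis and Section 3.1. State that, if the Cohort 1 range is expanded, the existing two-of-five trigger for DSMB review before further enrolment is counted afresh in the first five subjects entering above the original range. If the DSMB plan already provides this, a cross-reference is enough. Say also what happens if fewer than five such subjects accrue.

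This reuses the protocol's own DSMB, events and threshold. It changes no dose, titration step or individual stopping criterion.

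The cost is a wording amendment, possibly one extra DSMB meeting, and a short enrolment hold if the trigger is met. With only 5-10 later subjects, a hold could affect a large part of the remaining Cohort 1 enrolment.

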2 OBJECTIVES

2.1 PRIMARY OBJECTIVE

To assess the safety and tolerability of oral treprostinil extended release tablets in three cohorts of pediatric subjects with PAH aged 7 to 17 years:

- Cohort 1: Subjects transitioning from IV/SC Remodulin
- Cohort 2: Subjects transitioning from inhaled prostacyclin
- Cohort 3: As add-on to current PAH therapy in de novo prostacyclin subjects

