8.2 CRITERIA FOR TERMINATING THE STUDY

The study may be stopped at any time if, in the opinion of the Investigator and/or Sponsor, continuation of the study represents a serious medical risk to the subjects. This may include, but is not limited to, the presence of serious, life-threatening, or fatal AEs or AEs that are unacceptable in nature, severity, or frequency. The Sponsor reserves the right to discontinue the study for any reason at any time.

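### The only event-driven DSMB trigger in the protocol and SAP counts PAH worsening alone, although the primary objective is safety and tolerability

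*Protocol*

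**What the plan says.** Protocol 2.1 gives the primary objective: "To assess the safety and tolerability of oral treprostinil extended release tablets in three cohorts". Protocol 5.4 lists two stopping criteria. The first is "Unplanned hospitalization as a result of worsening PAH". The second is "Clinically significant worsening in PAH symptoms or signs, which the Investigator feels requires a change of current therapy". They are introduced with a time window, "If any of the following events occur within the four weeks following the first dose", after which it is not mandatory to take the child out of the study.

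The same section then makes these criteria the cohort-level trigger: "If two or more of the first five subjects in any cohort meet the stopping criteria, the data will be reviewed" by the DSMB before that cohort enrols further. The synopsis and Protocol 3.1 and 10.4 repeat the rule, as does SAP 5: "if 2 or more of the first 5 subjects within any cohort meet the pre-specified stopping criteria, the DSMB will review the data". None of them adds an event.

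There is one scheduled look, in Protocol 10.4: "Once five subjects have enrolled in Cohort 1 and transitioned from IV/SC Remodulin, the safety data will be reviewed by the DSMB". It does not depend on any event having occurred, and the Cohort 1 entry dose range may be widened only after it. SAP 5 says this meeting is to consider any safety concerns, and that its data will be prepared under a separate DSMB analysis plan.

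Protocol 8.2 gives as possible grounds for stopping the study "the presence of serious, life-threatening, or fatal AEs or AEs that are unacceptable in nature, severity, or frequency". The decision rests on the opinion of the Investigator and/or Sponsor, and the DSMB is not mentioned.

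**The concern.** The trigger is the device that brings an independent board in early when a cohort is going badly, and it recognises only one way of going badly: the disease getting worse. A child who stops oral treprostinil because the prostacyclin effects are intolerable, a child with a drug-related SAE unconnected with PAH worsening, or a child who dies without a prior PAH hospitalisation or a worsening that called for a change of therapy does not advance the count.

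These are the outcomes that a safety and tolerability objective is about. Under Protocol 10.3.1, success requires being clinically maintained on oral treprostinil through Week 24, so a child who stops early for intolerance is a failure on the primary endpoint and still invisible to the trigger. The gap weighs most in Cohorts 2 and 3, where no DSMB review is timed to enrolment.

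**Working it through.** **1. Which events reach the DSMB under the written text**

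- PAH worsening (either criterion in Protocol 5.4): counted toward two-of-five.
- Serious or life-threatening AE: Protocol 8.1 lists it as a reason for withdrawal separate from meeting the stopping criteria. The protocol therefore treats the two as different things, and such an AE is not counted unless it also meets a criterion.
- Withdrawal for intolerance: not among the stopping criteria, so not counted.
- Death: Protocol 9.1.4 requires every death to be reported as an SAE, with no link to the DSMB. It counts only if the course leading to it met one of the two criteria.
- Any event among the early Cohort 1 children: open to the scheduled review, because of an enrolment milestone and not because the event occurred.

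**2. How many children the trigger covers**

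First five in each of three cohorts: 3 × 5 = 15 of 40 at most (37.5%), leaving at least 25 outside it. In Cohorts 2 and 3 together: 2 × 5 = 10.

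**3. What the omission does to the chance of a referral**

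The documents give no operating characteristic for the rule and no event rates, so there is no stated figure to reproduce. The rates below are assumptions. With independent children and a common rate p,

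P(at least 2 of 5) = 1 − (1 − p)^5 − 5p(1 − p)^4.

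| Assumed rate p of the uncounted events | (1 − p)^5 | 5p(1 − p)^4 | P(rule fires) if counted | Contribution under the written rule |
|---|---|---|---|---|
| 10% | 0.59049 | 0.32805 | 0.081 | none |
| 20% | 0.32768 | 0.40960 | 0.263 | none |
| 30% | 0.16807 | 0.36015 | 0.472 | none |
| 40% | 0.07776 | 0.25920 | 0.663 | none |

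The last column follows from the definition; it is not a result.

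The nearest figure in the documents is the adult 12-week placebo-controlled study in Protocol 1.2.4, with all-cause discontinuation of 17% on drug and 14% on placebo. At p = 0.17 the formula gives 1 − 0.39390 − 0.40340 = 0.203. This is an imperfect proxy: it comes from adults, covers all causes, and includes some disease worsening.

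**4. Both kinds of event together**

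Assume PAH worsening at rate w and the uncounted events at rate o, without overlap. The written rule fires at p = w; a widened rule fires at p = w + o.

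| w | Written rule | Widened, o = 10% | o = 20% | o = 30% |
|---|---|---|---|---|
| 5% | 2.3% | 16.5% | 36.7% | 57.2% |
| 10% | 8.1% | 26.3% | 47.2% | 66.3% |

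**5. The time window**

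The four-week window in 5.4 governs mandatory removal of the individual child. The text does not say whether a qualifying event after Week 4 counts toward two-of-five.

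**The case against.** The case against has several sound parts.

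- *The trigger is not the only DSMB review.* The Cohort 1 review is unconditional, and the SAP gives it a broad safety purpose. Nothing expressly confines it to Cohort 1 data, so a reader who infers that the trigger is the only route by which the board could see Cohort 2 or 3 data goes further than the text. What stands is that no review is timed to enrolment in those cohorts.
- *A DSMB analysis plan exists and was not supplied.* It may contain further triggers. SAP 5 describes it only as governing how the safety data are prepared, but the gap is shown for the protocol and SAP alone.
- *Other oversight exists.* A reader might infer that several children could die or stop for toxicity while enrolment went on with nobody independent aware. The documents do not support that. SAEs go to the sponsor within 24 hours and promptly to the IRB (Protocol 9.4), serious unexpected events possibly attributable to the drug go to regulators and all investigators (9.6), and each new child needs sponsor permission before Baseline assessments (7.1, 7.3). None of this is DSMB review, but it is not silence.
- *Some toxicity could be counted.* Syncope is a scored PAH symptom (3.3.1.4) and appears in Table 9-1, so a hypotensive syncope could be judged to meet the second criterion. In Cohort 2, which is weaned off inhaled therapy, PAH worsening is itself a natural early risk.
- *The rates have no source.* Nothing in the documents shows that 30% or 40% is to be expected.
- *The study is descriptive,* and the drug is approved in adults, with more than 1,800 subjects exposed.

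These points narrow the concern without closing it. No clause in either document sends an intolerance withdrawal, or a drug-related SAE that is not PAH worsening, to the DSMB because it happened.

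**Conclusion.** The concern holds in a limited form. The one event-driven DSMB trigger in the protocol and SAP counts PAH worsening only, so it leaves out the toxicity and tolerability outcomes that the primary objective names. A single milestone-based Cohort 1 review partly compensates, and nothing equivalent is timed to Cohorts 2 or 3.

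The size should not be overstated. It is tempting to apply the gap to every child in Cohorts 2 and 3, but the trigger reaches only ten of them at most. The loss in referral probability runs from about 8 to 66 percentage points over assumed rates of 10% to 40% for the uncounted events taken alone, and is about 20 points at the adult all-cause discontinuation figure. These values depend on the assumed rates and on independence between children.

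Severity: should be fixed. Confidence is moderate, because the DSMB analysis plan was not available. No estimate is biased and the documents do not contradict each other here; the weakness is in what the safeguard is told to look for.

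**What to change.** Amend Protocol 5.4 and 10.4 and SAP 5, and mirror the change in the DSMB analysis plan, for the DSMB review trigger only:

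1. Count toward two-of-five, besides the two PAH-worsening criteria, any SAE rated possibly or probably related (the categories in Protocol Appendix 15.4) and any permanent discontinuation of oral treprostinil for an AE.
2. Refer any death to the DSMB on its own. Merely adding deaths to a two-of-five count would leave a single death without a referral.
3. State whether events after Week 4 count toward the trigger.

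If the DSMB analysis plan already covers these events, a cross-reference from the protocol and SAP is enough. The individual-subject stopping and treatment rules stay as they are. Non-fatal events after the fifth child in a cohort would still lie outside the trigger, and the sponsor should say whether that is intended.

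Cost: a protocol amendment, which under Protocol 13.1 needs regulatory and IRB approval, at about 10 centres; matching text in the SAP and DSMB plan; and possibly one or two extra DSMB reviews with short enrolment pauses.
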